1 PROTOCOL SUMMARY

1.1 Synopsis

Date and Version of Protocol Synopsis:		21 Jul 2021, Version 3.0
Sponsor: Astellas Pharma Inc. (API)		Protocol Number: 5354-CL-0201
Compound Name: ASP5354		Phase of Development: Phase 2
Title of Study: A Phase 2 Randomized Open-label, Dose-ranging Study for Ureter Visualization, Using ASP5354 in Subjects Undergoing Laparoscopic/Minimally Invasive Colorectal Surgery		
Planned Study Period: From approximately 1Q2020 to 4Q2021.		
Study Objectives and Endpoints:		
Objectives		Endpoints
Primary		

 To determine the optimal dose of ASP5354 for ureter visualization in subjects undergoing laparoscopic/minimally invasive colorectal surgery. 		
 Anatomical visualization of the index ureter(s) 30 minutes after dosing of ASP5354 and the end of surgery (Yes/No).
Secondary		

 To investigate the safety and tolerability of ASP5354 in subjects undergoing laparoscopic/minimally invasive colorectal surgery. To investigate the pharmacokinetics of ASP5354 in subjects undergoing laparoscopic/minimally invasive colorectal surgery. 		
Safety and Tolerability
 
 Vital signs (blood pressure, pulse and respiratory rate) Routine 12-lead electrocardiograms (ECGs) Clinical laboratory tests (hematology [complete blood count], serum chemistry and urinalysis) Nature, frequency and severity of treatment-emergent adverse events (TEAEs) and serious adverse events 
Pharmacokinetics
 
 Plasma and urine concentrations of ASP5354 Amount of ASP5354 excreted in urine (Ae) during surgery Percentage of drug dose excreted into urine (Ae%) during surgery
Table continued on next page		

Objectives	Endpoints																
Exploratory																	

 To investigate the relationship between pharmacokinetics and pharmacodynamics of ASP5354 in subjects undergoing laparoscopic/minimally invasive colorectal surgery. To explore fluorescence intensity and visualization duration of ASP5354 in subjects undergoing laparoscopic/minimally invasive colorectal surgery. To explore the benefit of visualization during surgery of ASP5354 in subjects undergoing laparoscopic/minimally invasive colorectal surgery. 	
 The Likert Scale for qualitative response about the intensity of fluorescence at the predefined time points during surgery Duration of anatomical visualization of the index ureter(s) from the first time of positive visualization to the last time point of positive visualization Signal background ratio (SBR) Binary questions (Yes/No) for the benefit of visualization by ASP5354 during surgery Ability to visualize the contralateral ureter when amenable to visualization 																

Ae: amount of ASP5354 excreted in urine; Ae%: percentage of drug dose excreted into urine; BMI: body mass index; ECGs: electrocardiograms; SAEs: serious adverse events; SBR: signal background ratio; TEAEs: treatment-emergent adverse events
																	

Planned Total Number of Study Sites and Location(s):
																	

Approximately 2 study sites in the US
																	

Study Population:
																	

Male or female subjects ≥ 18 years of age scheduled to undergo laparoscopic/minimally invasive colorectal surgery.
																	

Number of Subjects to be Enrolled/Randomized:
																	

  
 Dose Arm	ASP5354 Dose Level	Number of Subjects	
   
 1	CC1	Up to 15	
 
 2	CC2	Up to 15	
 
 3	CC3	Up to 15	
 
 Total	-	Up to 45	
  
			Dose Arm	ASP5354 Dose Level	Number of Subjects	1	CC1	Up to 15	2	CC2	Up to 15	3	CC3	Up to 15	Total	-	Up to 45
Dose Arm	ASP5354 Dose Level	Number of Subjects															
1	CC1	Up to 15															
2	CC2	Up to 15															
3	CC3	Up to 15															
Total	-	Up to 45															

  
 Additional Dose Arm	ASP5354 Dose Level	Number of Subjects	
   
 4	CC4	Up to 15	
 
 5	CC5	Up to 15	
 
 6	CC6	Up to 15	
  
			Additional Dose Arm	ASP5354 Dose Level	Number of Subjects	4	CC4	Up to 15	5	CC5	Up to 15	6	CC6	Up to 15			
Additional Dose Arm	ASP5354 Dose Level	Number of Subjects															
4	CC4	Up to 15															
5	CC5	Up to 15															
6	CC6	Up to 15															

* Based on VRC review of the initial 3 dose levels, if none of the doses selected have visualization, then CC1 and CC2 dose levels will be added; if 1 dose selected has visualization, then the CC3 dose level will be added. The CC4 dose level will only be added if only the CC3 dose level has visualization.
																	

Study Design Overview:
																	

The study is a randomized open-label, dose-ranging study in adult subjects undergoing laparoscopic/minimally invasive colorectal surgery in which the need for anatomical visualization of the ureter is anticipated.
																	

Subjects will be randomly assigned to receive single doses of ASP5354 (CC1, CC2 or CC3) which will be administered as an iv bolus to evaluate the anatomical visualization of the index ureter(s) (and contralateral ureter when feasible). Safety, tolerability and pharmacokinetics in the study population will also be assessed.
																	

Up to 15 subjects will be randomly assigned at each dose level. During a standard minimally invasive surgery, visualization of the surgical field will be assessed following the placement of the near-infrared fluorescence (NIR-F) imaging system (with FDA 510[k] cleared optical device system) proximal to the ureter of interest and then ASP5354 will be administered.
																	

 Intraoperative ureter fluorescence visualization will be assessed at approximately 10, 20, 30, 45 and 60 minutes post administration of ASP5354, and then every 30 minutes thereafter and/or at the last time point before removal of visualization instruments (end of surgery). 																	

- The contralateral ureter will also be visualized when feasible, per the investigator's judgment, at similar time points. Fluorescence images will be captured on a bright field, NIR-F and overlay view (if available) and recorded during the entire surgery and archived.
- The anatomical visualization of the index ureter(s) will be assessed by the investigator intraoperatively using a binary "Yes or No" question on the ability to visualize the ureter at each time point.
- The fluorescence intensity of the ureter will be qualitatively assessed using a Likert Scale (0 = None, 1 = Mild, 2 = Moderate and 3 = Strong).
- The duration of anatomical visualization of the index ureter(s) will be from the first time of positive visualization to the last time point of positive visualization.
- Recorded images will be used to determine the SBR.

The visualization data will be assessed by a Visualization Review Committee (VRC), consisting of the investigator(s) and the sponsor's medical representative. The VRC will be held at the following time points, but ad-hoc meetings may occur until the optimal dose is determined:

- 1) after the initial 3 subjects have completed the surgical procedures at each of the dose levels; and
- 2) then in increments of 3 subjects (up to a total of 15 subjects per dose level) for those who have completed surgical procedures at the expanded dose levels.

The visualization data for the subjects, at each interim time point, who completed the surgical procedure will be assessed to decide whether to:

- 1) expand a dose under evaluation;
- 2) stop a dose under evaluation in which case additional subjects would not be added to a dose level; or
- 3) define a dose as optimal.

Once the optimal dose is determined, the optimal dose cohort may continue enrollment up to the maximum 15 subjects.

The VRC assessment to stop, to continue or to define an optimal dose level will be based on the totality of the collected data, including but not limited to the following:

- 1) anatomical visualization of the ureter at both 30 minutes after ASP5354 administration and at the end of surgery, or
- 2) fluorescence intensity based on the Likert Scale (0 to 3).

In the case where 2 doses perform equally, the lower dose may be selected.

Based on VRC review of the initial 3 dose levels, if none of the doses selected have visualization, then **CC1** and **CC2** dose levels will be added; if 1 dose selected has visualization, then the **CC1** dose level will be added. The **CC2** dose level will only be added if only the **CC1** dose level has visualization. For further details of the VRC, refer to the VRC charter.

If the investigator judges that anatomical visualization of ASP5354 is not sufficient for the subject at 30 minutes after administration, the investigator can proceed with surgery using other modalities for visualization.

Safety and tolerability will be assessed by recording TEAEs and adverse reactions associated with the use of an investigational product (IP), clinical laboratory evaluations (hematology, serum chemistry and urinalysis), 12-lead ECGs, vital signs measurements and physical examination. Blood and urine samples for pharmacokinetic assessment will be collected pre- and post-administration of ASP5354 at defined time points, up to the end of surgery. In cases where surgery is completed in less than 105 minutes, blood samples will also be collected at 180 minutes after administration.

Inclusion/Exclusion Criteria:

Inclusion Criteria:

1. Institutional Review Board (IRB)/Independent Ethics Committee (IEC) approved written informed consent and privacy language as per national regulations (e.g., Health Insurance Portability and Accountability Act authorization for US study sites) must be obtained from the subject prior to any study-related procedures (including withdrawal of prohibited medication, if applicable).
2. Subject is scheduled to undergo laparoscopic/minimally invasive colorectal surgery.
3. Subject will need visualization of the ureter(s).
4. Subject is considered an adult (≥ 18 years of age) according to local regulation at the time of signing the informed consent form.
5. Female subject is not pregnant (see [Appendix 12.3 Contraception Requirements]) and at least 1 of the following conditions apply:
 - a. Not a woman of childbearing potential (WOCBP; see [Appendix 12.3 Contraception Requirements])
 - b. WOCBP who agrees to follow the contraceptive guidance (see [Appendix 12.3 Contraception Requirements]) from the time of informed consent through at least 30 days after final study treatment administration.
6. Female subject must agree not to breastfeed starting at screening and throughout the study period.
7. Female subject must not donate ova starting at first dose of IP and throughout the study period and for 30 days after final study treatment administration.
8. Male subject with female partner(s) of childbearing potential (including breastfeeding partner) must agree to use contraception (see [Appendix 12.3 Contraception Requirements]) throughout the treatment period and for 30 days after final study treatment administration.
9. Male subject must not donate sperm during the treatment period and for 30 days after final study treatment administration.
10. Male subject with pregnant partner(s) must agree to remain abstinent or use a condom for the duration of the pregnancy throughout the study period and for 30 days after final study treatment administration.
11. Subject agrees not to participate in another interventional study while participating in the present study.

Subjects enrolled after optimal dose determination:

12. Subject has any of the following values:
 - Body mass index > 25
 - Estimated glomerular filtration rate (eGFR) ≥ 15 mL/min/1.73 m² and < 60 . Subjects with an eGFR ≥ 60 mL/min/1.73 m² may be considered after discussion with the medical monitor.

Waivers to the inclusion criteria will **NOT** be allowed.

Exclusion Criteria:

1. Subject is anticipated to require ureteral stenting during surgery.
2. Subject has a history of known retroperitoneal fibrosis.
3. Subject has an active urinary tract infection.
4. Subject has received investigational therapy within 28 days or 5 half-lives, whichever is longer, prior to screening.
5. Subject has any condition that, in the investigator's opinion, makes the subject unsuitable for study participation.
6. Subject has a known or suspected hypersensitivity to ASP5354, indocyanine green (ICG) or any components of the formulation used.
7. Subject has had previous exposure to ASP5354.
8. Subject has moderate to severe cardiac disease that limits daily functioning (New York Heart Association Class III-IV) or other medical conditions that the investigator feels would impact safety or study compliance.
9. Subject has a mean resting heart rate ≤ 45 bpm or ≥ 115 bpm, mean systolic blood pressure ≥ 160 mmHg or mean diastolic blood pressure ≥ 100 mmHg on day -1. If the mean blood pressure exceeds the limits above, repeat readings can be taken. Subject who has adequately controlled blood pressure is eligible.
10. Subject has a mean corrected QT interval (Triplicate ECG) using Fridericia's formula (QTcF) > 430 msec (for male subjects) and > 450 msec (for female subjects) on day -1. If the mean QTcF exceeds the limits above, the mean of 1 additional triplicate ECG can be taken.
11. Subject has any of the following screening laboratory values:
 - Hemoglobin ≤ 9 g/dL
 - Absolute neutrophil count $\leq 1500/\mu\text{L}$
 - Platelet count $\leq 100000/\mu\text{L}$
 - eGFR < 60 mL/min/1.73 m² (Not applicable to subjects enrolled after optimal dose determination.)
 - Serum bilirubin $\geq 2 \times$ upper limit of normal (ULN)
 - Aspartate aminotransferase or serum glutamic oxaloacetic transaminase $\geq 2.5 \times$ ULN
 - Alanine aminotransferase or serum glutamic pyruvic transaminase $\geq 2.5 \times$ ULN
12. Subject has taken ICG or other NIR-F imaging agents within 48 hours prior to study treatment administration.
13. Subject has taken diuretics or inhibitors of renal transporters defined by FDA (see [Appendix 12.6 List of Excluded Concomitant Medications]) within 48 hours prior to study treatment administration.
14. Subject has used any illicit drugs, unless legally prescribed and is not being abused (amphetamines, barbiturates, benzodiazepines, cannabinoids, cocaine and opiates) within 30 days prior to day -1.
15. Subject has a history of alcohol abuse. Subject should not have consumed any alcohol within 48 hours of surgery.

Waivers to the exclusion criteria will **NOT** be allowed.

Investigational Product:

Name:

ASP5354

[figure not shown]
Use:

ASP5354 solution for administration will be supplied by the sponsor or designee as a CCI aqueous solution for iv administration. The NIR-F intensity of ASP5354 will be measured at wavelength 820 nm when irradiated with near-infrared excitation light at wavelength 780 nm.

Dose(s): ASP5354, CC1, or CC2 will be administered as a single dose once the surgical area of interest is in view.
 
Mode of Administration: ASP5354 will be administered as a single iv bolus administration under fasting conditions.

Dose Modifications: Since this is a single dose study, dose modification is not applicable.

Concomitant Treatment (Medication and Nonmedication Therapy) Restrictions or Requirements: The following concomitant medications will not be allowed from 48 hours prior to the IP administration until the completion of the surgical procedure:
 
● ICG unless used for anastomotic evaluation● Other NIR-F imaging agent● Diuretics● Inhibitors for renal transporters defined by FDA (see [Appendix 12.6 List of Excluded Concomitant Medications])

Duration of Treatment: Each subject will receive a single dose of ASP5354.

Treatment Discontinuation Criteria: Since this is a single dose study, treatment discontinuation is not applicable.

Statistical Methods: Sample Size Justification: The sample size is expected to provide adequate information to determine the optimal dose of ASP5354 for ureter visualization. This sample size is not based on statistical power calculation.


Efficacy: The success rate of anatomical visualization of the index ureter(s) 30 minutes after dosing of ASP5354 and at the end of surgery will be estimated with exact 95% confidence interval for the full analysis set (FAS). The FAS consists of all randomized subjects who receive ASP5354 and have at least 1 assessment of ureter visualization during surgery. The FAS will be used for the summary of efficacy.
 
Safety and Tolerability: The safety and tolerability endpoints will be summarized by descriptive statistics for the safety analysis set (SAF). The SAF consists of all randomized subjects who receive ASP5354.
 
Pharmacokinetics: A listing and summary statistics of the individual plasma and urine concentrations and sampling times by treatment and assessment time interval will be prepared. A total of Ae, Ae% and urine volume during surgery will be listed and summarized by treatment. Pharmacokinetic parameters will be evaluated by a population pharmacokinetic approach. Details of population analyses will be described in a separate analysis plan and a separate report.

Pharmacodynamics: The relationship between ureter visualization (Yes/No, Likert Scale, visualization duration, etc) and pharmacokinetics will be evaluated by a population pharmacokinetic/pharmacodynamic approach. Details of the population analyses will be described in a separate analysis plan and a separate report.

Interim Analyses: The determination of dose(s) to stop, continue or define a dose as optimal will occur when every 3 subjects randomly assigned to each dose level have the data for anatomical visualization during surgery reviewed via the VRC. The VRC will be held to review subject data until an optimal dose is determined.

1.2 Study Schema

[figure not shown]
Figure 1 Study Schema

BMI: body mass index; eGFR: estimated glomerular filtration rate; iv: intravenous; n: number of subjects; VRC: Visualization Review Committee

- Up to 15 subjects will be randomly assigned to receive single doses of ASP5354 at each dose level ([redacted] **CC1**). Once the optimal dose is determined, the optimal dose cohort may continue enrollment up to the maximum 15 subjects.
- Based on VRC review of the initial 3 dose levels, if none of the doses selected have visualization, then [redacted] **CC1** and [redacted] **CC2** dose levels will be added; if 1 dose selected has visualization, then the [redacted] **CC1** dose level will be added. The [redacted] **CC2** dose level will only be added if only the [redacted] **CC1** dose level has visualization.

Figure 2 Dose Cohort Schema

BMI: body mass index; VRC: Visualization Review Committee

- VRC will be held at the following time points, but ad-hoc meetings may occur: 1) after the initial 3 subjects have completed the surgical procedures at each of the dose levels; and 2) then in increments of 3 subjects (up to a total 15 subjects per dose level) for those who have completed the surgical procedures at the expanded dose levels.
- The visualization data for the subjects, at each interim time point, who completed the surgical procedure will be assessed to decide whether to: 1) expand a dose under evaluation; 2) stop a dose under evaluation in which case additional subjects would not be added to a dose level; or 3) define a dose as optimal. Visualization should occur at 30 minutes post ASP5354 administration and end of surgery and Likert Scoring (0 to 3) for each time point should be recorded. Once the optimal dose is determined, the optimal dose cohort may continue enrollment up to the maximum 15 subjects.

1.3 Schedules of Assessments

Table 1 Schedule of Assessments

Assessments	Screening Period	Treatment Period			Follow-up Period
	Day -28 to -1	1 (Operation)			7 (Outpatient) ¹³
Window	-	Preoperative	Intraoperative	Postoperative	+3
Visit Number	1	2			3
Informed Consent	X				
Inclusion/Exclusion Criteria	X				
Medical History	X				
Demographics	X				
Drug and Alcohol Screen ¹	X [†]				
Randomization		X			
Physical Examination ²	X	X		X	X
Vital Signs ³	X	X		X ¹²	X
Clinical Laboratory Tests ⁴	X [†]	X		X ¹²	X
Height and Body Weight ³	X				X
Serum Pregnancy Test ⁵	X [†]				X
Routine 12-lead ECG ⁶	X	X		X	X
Dosing ASP5354			X		
Blood Sampling for ASP5354 Pharmacokinetics and Metabolite Profiling ⁷		X	X	X	
Urine Point Sampling for ASP5354 Pharmacokinetics and Metabolite Profiling ⁷		X	X		
Total Urine Sampling in Catheter Bag and Amount of ASP5354 Excreted in Urine During Surgery ⁸			X		
Confirmation of urine discoloration ⁹			→	→	→
Investigator Evaluation for Ureteral Visualization ¹⁰			X		
Record Surgery			X ¹¹		
Previous/Concomitant Medications	X	X	X	X	X ¹⁴
AE Assessment	X	X	X	X	X ¹⁴

AE: adverse event, ECG: electrocardiogram

†These assessments will be performed by local laboratory and the results of these assessments have to be obtained prior to subject randomization.

Footnotes continued on next page

1. Drug screen (e.g., amphetamines, barbiturates, benzodiazepines, cannabinoids, cocaine and opiates) and alcohol screen will be performed by the study site's preferred method.
2. A full physical examination will be performed at screening (visit 1). Body systems to be evaluated include general appearance, skin, lymphatic, head and neck, ears, nose and throat, chest and lungs, cardiovascular, abdomen, extremities, musculoskeletal and neuromuscular. At visit 2 and follow-up (visit 3), a symptom-directed physical examination will be performed.
3. Vital signs include blood pressure, pulse and respiratory rate. All vital signs will be measured with the subject in the sitting or supine position. Height and weight will be measured using standard institution practice and equipment.
4. Clinical laboratory tests include blood collection for hematology (complete blood count) and serum chemistry and urine samples for urinalysis.
5. This assessment will be required only for subjects who are women of childbearing potential (see [Appendix 12.3 Contraception Requirements]).
6. Routine 12-lead ECGs will be taken in triplicate.
7. Blood and urine samples for pharmacokinetics of investigational product and possible metabolite(s) (if applicable) will be collected from every subject. A single pharmacokinetic blood sample will be collected at each of the following time points: prior to dose, approximately 10 minutes postdose, either approximately 30 or 60 minutes postdose and at the end of surgery. In cases where surgery is completed in less than 105 minutes, blood samples will also be collected at approximately 180 minutes after administration. Urine point sampling will be performed prior to dose and at the end of surgery (the end of surgery is an optional time point if a sample is available). For a detailed procedure of pharmacokinetic sampling, refer to the Sample Handling and Processing Manual.
8. Total urine volume of urine in the catheter bag will be calculated by dividing the weight of urine in the catheter bag by predefined density. Urine volume will be recorded in millimeters, and urine sample for pharmacokinetics of investigational product and possible metabolite(s) (if applicable) will be collected from the urine in the catheter bag to calculate Ae and Ae%. For a detailed procedure of total urine volume calculation, refer to the Sample Handling and Processing Manual.
9. The incidence of green discoloration of the urine will be recorded any time after dose administration. If it occurs, the color of urine will be assessed during surgery and every 120 minutes (\pm 30 minute window) after the end of surgery until it resolves or the subject is discharged, whichever is earlier. The start and stop date and time will also be recorded.
10. Surgeon evaluation for ureteral visualization includes incidence of anatomical visualization of the ureter(s), questions for the surgical benefit of ASP5354 and the Likert Scale for qualitative response about the intensity of fluorescence at the predefined time points during surgery.
11. Fluorescence images will be captured and recorded during the entire surgery and archived.
12. Postoperative vital signs and clinical laboratory tests will be collected within 2 hours after the surgery.
13. If a subject discontinues early from the study, day 7 outpatient visit procedures will be performed upon discontinuation.
14. If a subject experiences an AE or change in concomitant medications during days 2 to 6, he or she should call the study site to inform any of these changes. Should subjects develop a hypersensitivity reaction, an additional blood sample for determination of histamine and tryptase concentrations should be taken as soon as possible after the onset of the hypersensitivity reaction.

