5.1 Inclusion Criteria

Subject is eligible for participation in the study if all of the following apply:

1. Institutional Review Board (IRB)/Independent Ethics Committee (IEC) approved written informed consent and privacy language as per national regulations (e.g., Health Insurance Portability and Accountability Act authorization for US study sites) must be obtained from the subject prior to any study-related procedures (including withdrawal of prohibited medication, if applicable).
2. Subject is scheduled to undergo laparoscopic/minimally invasive colorectal surgery.
3. Subject will need visualization of the ureter(s).
4. Subject is considered an adult (≥ 18 years of age) according to local regulation at the time of signing the informed consent form (ICF).
5. Female subject is not pregnant (see [Appendix 12.3 Contraception Requirements]) and at least 1 of the following conditions apply:
 - a. Not a woman of childbearing potential (WOCBP; see [Appendix 12.3 Contraception Requirements])
 - b. WOCBP who agrees to follow the contraceptive guidance (see [Appendix 12.3 Contraception Requirements]) from the time of informed consent through at least 30 days after final study treatment administration.
6. Female subject must agree not to breastfeed starting at screening and throughout the study period.
7. Female subject must not donate ova starting at first dose of IP and throughout the study period and for 30 days after final study treatment administration.
8. Male subject with female partner(s) of childbearing potential (including breastfeeding partner) must agree to use contraception (see [Appendix 12.3 Contraception

Requirements]) throughout the treatment period and for 30 days after final study treatment administration.

9. Male subject must not donate sperm during the treatment period and for 30 days after final study treatment administration.
10. Male subject with pregnant partner(s) must agree to remain abstinent or use a condom for the duration of the pregnancy throughout the study period and for 30 days after final study treatment administration.
11. Subject agrees not to participate in another interventional study while participating in the present study.

Subjects enrolled after optimal dose determination:

12. Subject has any of the following values at screening:
 - Body mass index > 25

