5.2 Exclusion Criteria

Subject will be excluded from participation in the study if any of the following apply:

1. Subject is anticipated to require ureteral stenting during surgery.
2. Subject has a history of known retroperitoneal fibrosis.
3. Subject has an active urinary tract infection.
4. Subject has received any investigational therapy within 28 days or 5 half-lives, whichever is longer, prior to screening.
5. Subject has any condition that, in the investigator's opinion, makes the subject unsuitable for study participation.
6. Subject has a known or suspected hypersensitivity to ASP5354, ICG or any components of the formulation used.
7. Subject has had previous exposure to ASP5354.
8. Subject has moderate to severe cardiac disease that limits daily functioning (New York Heart Association Class III-IV) or other medical conditions that the investigator feels would impact safety or study compliance.
9. Subject has a mean resting heart rate ≤ 45 bpm or ≥ 115 bpm, mean systolic blood pressure (SBP) ≥ 160 mmHg or mean diastolic blood pressure (DBP) ≥ 100 mmHg on day -1. If the mean blood pressure exceeds the limits above, repeat readings can be taken. Subject who has adequately controlled blood pressure is eligible.
10. Subject has a mean corrected QT interval (Triplicate ECG) using Fridericia's formula (QTcF) > 430 msec (for male subjects) and > 450 msec (for female subjects) on day -1. If the mean QTcF exceeds the limits above, the mean of 1 additional triplicate ECG may be taken.
11. Subject has any of the following screening laboratory values:
 - Hemoglobin ≤ 9 g/dL

- Absolute neutrophil count $\leq 1500/\mu\text{L}$
 - Platelet count $\leq 100000/\mu\text{L}$
 - eGFR $< 60 \text{ mL}/\text{min}/1.73 \text{ m}^2$ (Not applicable to subjects enrolled after optimal dose determination.)
 - Serum bilirubin $\geq 2 \times$ upper limit of normal (ULN)
 - Aspartate aminotransferase (AST) or serum glutamic oxaloacetic transaminase $\geq 2.5 \times$ ULN
 - Alanine aminotransferase (ALT) or serum glutamic pyruvic transaminase $\geq 2.5 \times$ ULN
12. Subject has taken ICG or other NIR-F imaging agents within 48 hours prior to study treatment administration.
 13. Subject has taken diuretics or inhibitors of renal transporters defined by FDA (see [Appendix 12.6 List of Excluded Concomitant Medications]) within 48 hours prior to study treatment administration.

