7.2 Safety Assessments

Study procedures and their timing are summarized in the Schedule of Assessments [Table 1]. Protocol waivers or exemptions are not allowed.

Procedures conducted as part of a subject's routine clinical management (i.e., standard of care) obtained before signing the ICF may be utilized for screening or baseline purposes, provided the procedures met the protocol-specified criteria and were performed within the time frame, as defined in the Schedule of Assessments [Table 1].

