7.2.2 Laboratory Assessments

Laboratory assessments will be performed at a local laboratory. Blood samples will be collected via a peripherally or centrally placed iv cannula, an intra-arterial cannula or by direct venipuncture in a suitable vein.

Blood samples for hematology (complete blood count) and serum chemistry and urine samples for urinalysis will be collected as indicated in the Schedule of Assessments [Table 1]. The clinical laboratory tests to be performed in the study are listed in [Appendix 12.7 Laboratory Assessments].

Drugs of abuse (e.g., amphetamines, barbiturates, benzodiazepines, cannabinoids, cocaine and opiates) and alcohol tests will be performed on samples collected as indicated in the Schedule of Assessments [Table 1]. Drugs of abuse and alcohol tests will be performed according to the study site's preferred method.

Pregnancy tests will be performed on samples collected as indicated in the Schedule of Assessments [Table 1]. Pregnancy tests (WOCBP only) will be performed on serum samples.

The investigator or subinvestigator must review the laboratory report and document this review.

Clinical significance of out-of-range laboratory findings is to be determined and documented by the investigator or subinvestigator who is a qualified physician.

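### The last scheduled pregnancy test before dosing can be up to 28 days old, because Table 1 has no Day 1 recheck for women of childbearing potential

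*Protocol*

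**What the plan says.** Being non-pregnant is an eligibility condition: inclusion criterion 5 (Protocol Section 5.1) begins "Female subject is not pregnant". Table 1 (Protocol Section 1.3) has the row "Serum Pregnancy Test", restricted by footnote 5 to women of childbearing potential. It is marked at screening (Day -28 to -1) and at the Day 7 (+3) outpatient visit. Its Day 1 cells (preoperative, intraoperative, postoperative) are empty, and ASP5354 is given intraoperatively on Day 1.

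The only timing condition on the screening test is the dagger footnote: "the results of these assessments have to be obtained prior to subject randomization". It sets no maximum age for the result.

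Section 7.2.2 refers back to the schedule: "Pregnancy tests will be performed on samples collected as indicated in the Schedule of Assessments". Appendix 12.3 does the same, and also says that test results have to show the woman is not pregnant, without saying when. SAP Section 6.5.5 only lists the results.

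Contraception for women of childbearing potential is required "from the time of informed consent through at least 30 days after final study treatment administration" (criterion 5b).

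**The concern.** An eligibility condition for an investigational intravenous agent can rest on a result four weeks old, and the next scheduled test comes after exposure. For some other conditions the protocol does require recent values. Exclusion criterion 9 uses "mean diastolic blood pressure (DBP) ≥ 100 mmHg on day -1" together with heart rate and systolic limits, and criterion 10 sets the QTcF limits at "> 430 msec (for male subjects) and > 450 msec (for female subjects) on day -1".

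The contraception requirement narrows the gap but does not close it. It starts at consent, so it does not cover a conception shortly before consent that is too early for the screening test to detect. Section 7.2 also allows routine-care procedures "obtained before signing the ICF may be utilized for screening or baseline purposes", so part of the interval between test and dose can fall before contraception is required.

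What is at stake is avoidable exposure of an early pregnancy. The trial's statistical results are not at stake.

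**Working it through.** **Age of the test at dosing.** Table 1 gives a screening window of Day -28 to -1 and dosing on Day 1, and shows no Day 0.
- Test on Day -28: 28 days old at dosing.
- Test on Day -1: 1 day old at dosing.
- Scheduled tests between screening and dosing: 0.

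**Whether another section fills the gap.**
- Table 1, footnote 4: the clinical laboratory tests repeated preoperatively are hematology, serum chemistry and urinalysis. hCG is not among them.
- Appendix 12.7, Table 9: names serum hCG as a separate panel and gives no timing.
- Section 7.2.2 and Appendix 12.3: refer back to the schedule.
- Table 1, eligibility row: marked at screening only, so no scheduled Day 1 eligibility check catches it.
- SAP 6.5.5: a listing only.

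None adds a pre-dose test. Empty Day 1 cells between marks at screening and follow-up also occur in the height and weight row, so the pattern does not look like a fault of text extraction.

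**Size.** Inputs:
- Interval: 28 days for every woman (the maximum, from Table 1).
- Subjects: 45 (three initial arms of up to 15).
- Annual contraceptive failure: 1%, the ceiling that Appendix 12.3 gives for perfect use of highly effective methods; and 10%, an assumption. The appendix warns that typical use may differ but gives no figure.
- Share of women of childbearing potential: 5-20%, an assumption. The documents give none.

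Probability per woman = (28/365) × annual rate:
- at 1%: 0.0767 × 0.01 = 0.000767 (0.08%)
- at 10%: 0.0767 × 0.10 = 0.00767 (0.77%)

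Number of women: 0.05 × 45 = 2.25; 0.20 × 45 = 9.

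Expected conceptions = women × probability:

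| Annual failure | 2.25 women | 9 women |
|---|---|---|
| 1% | 0.0017 | 0.0069 |
| 10% | 0.017 | 0.069 |

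The range is about 0.002 to 0.07. It counts conceptions during the interval, not conceptions that a Day 1 test would find. Those in the last days before surgery would still be missed, so the benefit of the test against these conceptions is smaller than the table. Conceptions before consent that the screening test missed are not in the table, and the documents give nothing from which to estimate them.

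**The case against.** The strongest case against is that this is a preference about scheduling. Appendix 12.3 ties testing to the schedule, and the schedule is followed. Eligibility is confirmed at screening in general, and the laboratory limits of exclusion criterion 11 are screening values too. Exposure is a single dose, highly effective contraception is required from consent, and Section 2.1.2 reports no sign of embryofetal toxicity in the nonclinical species tested. The Day 7 test may reveal a pregnancy that was present at dosing, and Section 12.4.6.1 provides for reporting and follow-up. Sites may test before surgery anyway.

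Much of this stands, and it keeps the point small. It does not supply a pre-dose test: the Day 7 test and pregnancy reporting act only after exposure, and the documents do not describe the sites' own practice.

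Three stronger readings are tempting and are not supported:
- **That the protocol breaks its own rule, or treats pregnancy less strictly than other conditions.** Appendix 12.3 gives no time point, and criterion 11 works in the same way.
- **That results from before consent could be older than 28 days.** Section 7.2 accepts such procedures only if they meet the protocol's criteria and fall within the schedule's time frame.
- **That women will in practice go to surgery without a recent test.** The documents support only the absence of a protocol-scheduled one.

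**Conclusion.** The point holds as an optional improvement to the safety schedule. The last protocol-scheduled pregnancy result can be 1 to 28 days old at dosing, and nothing in the protocol or SAP shortens that. This follows directly from Table 1.

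The consequence is small: at most about 0.07 expected conceptions among 45 subjects under the stated assumptions, with every woman given the longest interval. That figure is an illustration, not an estimate of what the recheck would prevent. It rests on an assumed share of women of childbearing potential and an assumed 10% annual failure rate at the upper end. The conception too early for the screening test and not covered by contraception is the less tractable part and stays unquantified.

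No endpoint, analysis set or dose decision changes.

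**What to change.** In Table 1, mark a pregnancy test for women of childbearing potential in the Day 1 preoperative column. Use serum hCG, taken with the preoperative laboratory blood. If waiting for serum would delay surgery, use urine hCG on the preoperative urinalysis sample. Section 7.2.2 and Table 9 name serum only, so the urine option needs a matching word in both.

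Add a footnote requiring a negative result before ASP5354 is given, preferably before randomization. The footnote has to set that order itself: Section 6.3 says only that the assignment is obtained before treatment starts, and not whether the preoperative samples come first.

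The longest age of the last scheduled test then falls from 28 days to the same day. The gain is greatest when screening was weeks earlier and slight when it was on Day -1. The cost is one cell, one footnote, one added assay in a few women (about 2 to 9 of 45 under the assumption above), and possibly a short wait for the result on the day of surgery. The SAP needs no change, since its listing already covers all pregnancy tests.
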